### **5.1 Unilateral femoral approach**

Selective catheterization of the hepatic artery will be performed. Vascular access is obtained via the common femoral artery and a guide-wire advanced under fluoroscopy. A 5/6 F sheath is then inserted over a guide-wire. The superior mesenteric artery is selected and an angiogram performed to identify any aberrant arterial anatomy and verify antegrade portal vein flow. The celiac axis is then selected and an angiogram completed. The catheter and guide-wire are used to select proper hepatic artery and a limited angiogram performed to identify branches of the hepatic artery. The right and left hepatic is selected distal to the cystic artery if visualized, depending of the lesion to be treated using the appropriate catheter.

### **5.2 Super-selective chemoembolization**

5.2.1 Once vascular supply of the tumor is identified super-selective chemoembolization of the tumor supplying artery is performed with catheter positioned in second or third order side branches. If the anatomy is sufficiently visualized with fluoroscopy, and a cone-beam CT is available, a cone-beam CT will be performed to assess appropriate segmental contrast distribution covering the target.

5.2.2 TACE will be performed with (see Appendix C). Two vials of beads will be prepared with, per the discretion of the treating physician, 50mg of Doxorubicin. Iodine contrast will be mixed

according to manufacturer guidelines and used to guide the delivery. Bead size will be at the discretion of the treating physician.

5.2.3 TACE without doxorubicin will be performed in an identical manner. Bead size will be at the discretion of the treating physician.

5.2.3 Target area will be embolized until segmental arterial stasis is achieved. In the presence of multifocal disease selective catheter positioning will be repeated for each lesion.

5.2.4 If available, final cone-beam CT will be performed to document distribution of the embolic material.

5.3 Following the TACE procedure all subjects will remain in hospital per standard of care for extended recovery.

5.4 If stasis of arterial flow to the tumor(s) was not achieved, additional TACE treatments will be administered, each approximately 4-6 weeks after the prior TACE procedure was performed until stasis is achieved with a maximum of three TACEs administered as initial therapy. After the first TACE, any additional treatments will be performed per the discretion of the treating Interventional Radiology Team.

**Completed treatment will be defined by the date of the final TACE procedure considered as part of initial therapy (up to 3 TACE treatments).**

5.5 Progression of disease will be confirmed with imaging done greater than 8 weeks from last treatment date. Images collected per transplant protocol within the 8 weeks of treatment will be repeated, as per study schematic, to confirm response to treatment or progression.

If there is a radiological discrepancy regarding findings of residual, recurrent or progressive disease, the site must submit the subject's de-identified images to the centralized radiology panel overseen at LHMC. The panel will make the final determination and notify the site investigator. Any additional ablative treatment, be it to repeat TACE or SBRT or other therapy will be determined at that time. All treatment will be individualized by subject at the discretion of the transplant team.

5.6 Additional local treatment to the target lesion(s) in the assigned treatment arm:

Group 1: SBRT (Arm A), subjects with residual disease or local recurrence ***in the previously treated lesion(s)*** on radiologic imaging at any point in follow up will be considered as having met the primary endpoint of the trial and they are off the study. Patients may be considered candidates for additional local regional therapy to the treated lesion of any kind per the discretion of the treating.

Group 2: TACE (Arm B), subjects with residual disease or local recurrence ***in the previously treated lesion(s)*** on radiologic imaging at any point in follow up will be considered as having met the primary endpoint of the trial and they are off the study. Patients may be considered candidates for additional local regional therapy to the treated lesion(s) of any kind per the discretion of the treating providers.

5.7 Patients in either group who develop new ***intrahepatic lesion(s)*** at any point in follow up will ***not have met the primary endpoint as they have not progressed at the site of previous treatment.*** They may be considered candidates for additional local regional therapy to the new site of disease ***of any kind*** per the discretion of the treating providers and will be followed per Table 4 thereafter.

5.8 If patients have no evidence of progression or residual disease in the treated lesion(s) ***but develop new tumors outside the previously treated field*** and, per the discretion of the treating providers, require treatment with systemic therapy, the patient will be censored from the data analysis for the primary endpoint and will be discontinued from the study.

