#### 11.1.4 Ablative Therapy and Post-ablation imaging

If multiple TACEs are planned, participants need to first complete the entire treatment scheme per institutional SOC before undergoing response assessment. In some participants, the post-ablation imaging time point may occur closer than 90 days to the next serial imaging time point required for liver transplant waitlist updates. Sets of post-ablation imaging studies that are less than 90 days old at the time of the next scheduled UNOS HCC-exception point update (serial) images do not have to (but may) be repeated at the time of exception point update and may count towards the serial imaging time point for the purpose of the trial. For the remainder of the trial, these participants continue to be imaged according to the OPTN/UNOS schedule for updating HCC-exception points. Should another round of ablative treatment become necessary, the above rules apply for all post-ablation imaging sets and subsequent serial time points.

Serial MR or CT imaging will be performed at distinct time points as dictated by OPTN/UNOS until transplantation. Timing of serial SOC imaging in waitlisted patients is dictated by OPTN/UNOS HCC-exception point update requirements (90 day intervals). Waitlisted patients are defined as those eligible for/scheduled to undergo LDALT as well as those waiting for livers from deceased donors to become available. Postablation imaging studies that are less than 90 days old at the time of the next scheduled UNOS HCC exception point update (serial) images do not have to (but may) be repeated at the time of exception point update and may count towards the serial imaging time point for the purpose of the trial.

**11.2 Local intrahepatic tumor:** The status of each treated tumor/target lesion will be assessed by MRI or CT scan and classified as progression if there is tumor growth (excluding growth due to biloma or abscess formation), residual or new enhancement of the ablated tumor (excluding benign peri-ablational enhancement), or contiguous viable tumor. Each treated intrahepatic lesion will be evaluated utilizing mRECIST Criteria for HCC (Appendix B). All imaging will be assessed at the treating institution. If concern for residual or progressive disease is raised, imaging will be reviewed a second time at the individual institutions' multi-disciplinary conference review.

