## 16.0 Sample Size

This study is sized for hypotheses testing of improved time to residual or recurrent disease within the previously treated lesion(s) due to SBRT versus TACE treatment arms in the overall population of patients who are eligible for liver transplant and are on the waiting list. It is believed that more than 50% of patients will receive a transplant within 2 years of listing, but that far fewer patients will receive

a transplant within 1 year of study begin. Therefore we base power calculations on one year follow up and a drop rate of 15%. Based on initial data, we estimate a median time to residual or recurrent disease of 134 days in the TACE group. Based upon these numbers and a hazard ratio of 0.6 for the SBRT relative to the TACE group, a two-sided test controlling the overall type 1 error to 5% requires a total of 161 events (i.e. residual/recurrent disease) and about 131 patients per treatment arm to achieve a power of 90%. To achieve a power of 80%, a total of 120 events and about 98 patients per treatment arm are required. These calculations are made accounting for follow-up on patients once every three months where the calculated HR of 0.6 for this discrete model corresponds roughly to a HR of 0.54 if recurrent disease could be measured on the continuous time scale (days).

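### The boundary between initial TACE and retreatment has three different bases and no decision rule, so a TACE-arm lesion with residual tumor can be re-treated uncounted, with no SBRT equivalent

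*Combined protocol and SAP*

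**What the plan says.** Three passages bear on when a second or third TACE is given.

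- Section 5.4, procedural trigger: "If stasis of arterial flow to the tumor(s) was not achieved, additional TACE treatments will be administered". These follow at intervals of about 4-6 weeks, with at most three procedures as initial therapy.
- Section 5.4, next sentence: "After the first TACE, any additional treatments will be performed per the discretion of the treating Interventional Radiology Team".
- Section 11.1.4: "If multiple TACEs are planned, participants need to first complete the entire treatment scheme per institutional SOC before undergoing response assessment".

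Section 5.4 then dates completion of treatment to the last TACE regarded as belonging to initial therapy. It does not say who decides that, when, or on what evidence.

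Section 5.5 requires progression to be confirmed on imaging more than 8 weeks after the last treatment, and scans taken sooner are repeated. Section 5.6 applies one event rule to both arms: patients with residual disease or local recurrence in a treated lesion, at any point in follow-up, "will be considered as having met the primary endpoint of the trial and they are off the study".

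SBRT is a single course of five fractions within 15 days (section 4.4.3.1). In both arms time runs from randomization (section 13.1), and the trial is unblinded (section 15.0).

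**The concern.** The stated hypothesis concerns the interval from initial treatment to the need for retreatment, so the line between the two is central to the trial's question. In the TACE arm that line can be drawn after something is known about how the lesion responded. A team that sees viable tumor after a procedure that did reach stasis could give another TACE and regard it as part of the initial series. The lesion then has no event and the procedure is not a further intervention. An SBRT patient with residual disease has no second course to which this could apply.

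The existing safeguards would not clearly catch this. The central radiology panel sees images only when two local readings disagree (section 11.2). The TACE calendar (Table 3) lists no item for stasis or for the indication of a repeat procedure. Centers could also apply different rules. Affected are the primary endpoint, the number of further interventions, and the any-retreatment and number-of-retreatments comparisons in section 17.2.3.

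**Working it through.** **Plan's own figures (section 16.0, Table 7).** Inputs: "a hazard ratio of 0.6 for the SBRT relative to the TACE group"; "we estimate a median time to residual or recurrent disease of 134 days in the TACE group"; two-sided 5%; 80% power.

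- Events = 4(1.960 + 0.842)² / (ln 0.6)² = 4 × 7.849 / 0.2609 = 120.3, against 120 stated.
- Daily rates: TACE ln 2 / 134 = 0.005173; SBRT 0.6 × 0.005173 = 0.003104; dropout −ln(0.85) / 365 = 0.000445.
- One-year event probability = λ/(λ+η) × [1 − exp(−365(λ+η))], with λ the event rate and η the dropout rate: TACE 0.802, SBRT 0.635.
- Patients per arm = 120 / (0.802 + 0.635) = 83.5; divided by 0.85 this is 98.2. The plan states: "To achieve a power of 80%, a total of 120 events and about 98 patients per treatment arm are required".
- Expected TACE events under this model = 120 × 0.802 / 1.437 = 67.

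**Can a scheduled scan fall inside a TACE series?** Section 7.0 lets treatment start up to 3 weeks after randomization.

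- Start on day 21: TACE 2 falls on day 49-63 and TACE 3 on day 77 (4-week gaps) to 105 (6-week gaps).
- Start on day 0: TACE 3 falls on day 56-84.
- The Table 4 scan at 3 months ± 4 weeks, taking 3 months as 91 days, falls on day 63-119. It can precede TACE 3 in both cases, though with a day-0 start only when the gaps are toward 6 weeks.
- Patients not on the transplant list are scanned at four months ± 4 weeks (section 11.1.3.4). That window opens at about day 122 − 28 = 94, so overlap needs a late start and long gaps.

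For residual tumor on such a scan, section 5.6 points to an event if the scan counts as follow-up. Section 11.1.4 says response is not yet assessable, and section 5.5 requires a repeat more than 8 weeks after the last treatment, a date that another TACE moves. The heading of Table 4 places follow-up after the initial treatment phase, which leaves the status of the scan open.

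**Earliest confirmed event, day-21 start.**

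| Course | Calculation | After day |
|---|---|---|
| One TACE | 21 + 56 | 77 |
| Three TACEs, 4-week gaps | 21 + 56 + 56 | 133 |
| Three TACEs, 6-week gaps | 21 + 84 + 56 | 161 |
| SBRT, if section 5.5 applies to it | 21 + 15 + 56 | 92 |

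With a 134-day exponential median, 1 − exp(−0.005173 × t) is 50% at day 133 and 57% at day 161. About half or more of TACE events would be due before a three-TACE patient could have a confirmed one.

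**Bound on affected events.** The documents give no rate of repeat TACE after stasis. Assume 10-30% of 98, that is about 10-29 patients. If every such lesion would otherwise have been an event, 10/67 = 15% to 29/67 = 43% of TACE events are delayed or removed.

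**Illustration of power.** Simulation with 98 per arm, HR 0.6, 91-day scans, one-year accrual, two-year study, 15% yearly dropout and no transplant censoring. A share q of TACE residual disease arising in the first 91 days is re-treated without an event and the clock restarts at day 91.

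| q | Power, HR 0.6 | Power, HR 0.54 |
|---|---|---|
| 0 | 88% | 97% |
| 10% | 80% | 93% |
| 25% | 66% | 85% |
| 50% | 38% | 61% |

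The HR 0.6 starting point exceeds 80% because these settings yield about 151 events, not 120.

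**The case against.** The strongest reply is that section 5.4 does not say what a reader might infer, namely that any discretionary second or third TACE counts as initial therapy. The sentence before ties further TACE to non-stasis, and the three-procedure cap belongs to that condition. The discretion sentence may leave only the execution of the stasis rule to the team. Stasis is also an angiographic finding made during the procedure, not a reading of tumor response. This stands: the text is ambiguous and does not settle on the broad reading. But the ambiguity is itself the defect, since centers may resolve it differently.

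Second, Table 3 schedules no abdominal imaging between TACEs, so nobody need see the result of the first. This does not hold. The 3-month scan can precede a third TACE, and section 5.5 itself expects transplant-protocol scans within 8 weeks of treatment.

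Third, section 5.6 treats the arms alike, a series of up to three TACEs is disclosed openly, and the 8-week rule may mean that neither arm has a confirmed event early on. The shared wording and the disclosure are fair points, and a multi-procedure control is legitimate. What is missing is the rule for where the series ends. The 8-week rule sits in the TACE section, and its scope across arms is unstated.

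Fourth, the assumed share has no source, and re-treated patients remain at risk, so many events would be delayed rather than lost. Both points stand. In the illustration, q of 10% still leaves 80% power.

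**Conclusion.** The plan gives three bases for a repeat TACE and no rule for which procedures count as initial. It therefore permits, without clearly intending, uncounted re-treatment of residual tumor in one arm of an unblinded trial. The consequence is fewer or later TACE events and retreatments, a hazard ratio pulled toward 1, lower power, and counts that depend on center labelling.

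A reader might infer that the primary test is tilted toward SBRT or that type I error is inflated. The documents do not support this: hiding or delaying control events works against the SBRT superiority hypothesis. Since the test is two-sided, a result favoring TACE would also have to be read in light of the counting rule.

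The size cannot be derived from the documents. The 15-43% range is an upper bound. It rests on an assumed 10-30% share, on the one-year model behind the 98 per arm, and on every affected lesion otherwise being an event. The simulated power values are illustrations, not predictions. The matter should be settled in the protocol text.

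**What to change.** Change the counting and leave the clinical freedom to repeat TACE as it is.

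1. Reconcile sections 5.4, 5.5, 5.6 and 11.1.4 on when a further TACE belongs to initial therapy.
2. Record on the CRF, at the time of each procedure, stasis yes/no per lesion and the indication for any repeat TACE.
3. For analysis, count a repeat TACE to an already treated lesion as initial therapy only if non-stasis was documented at the preceding procedure. First treatment of a not-yet-treated lesion in a staged plan stays initial. Any other repeat is a further intervention.
4. State how imaging obtained before the last initial TACE is counted, consistently with the 8-week confirmation rule, and say whether that rule covers both arms.
5. Prespecify a sensitivity analysis of the primary endpoint in which a repeat TACE after documented stasis is an event.

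The cost is protocol wording, a few CRF items and one extra analysis. The small downside is that some repeat TACEs that centers regard as routine will be counted as further interventions.

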### 2.0 Secondary endpoints:

- Health related quality of life (HRQL) for both treatment arms
- Toxicity
- Number of further interventions
- Pathologic response of treated lesion(s)
- Radiologic response of treated lesion(s)
- 60 day Post-transplant morbidity and mortality

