## 6.0 Health Related Quality of Life (HRQL)

To assess HRQL, subjects will be assessed using the Functional Assessment of Cancer Therapy—Hepatobiliary (FACT-Hep) Questionnaire (Appendix D). This 45-item self-report instrument is designed to measure HRQL in patients with hepatobiliary cancers and is one of the most widely-used instruments in this clinical area. The FACT-Hep consists of the 27-item FACT-G, which assesses generic HRQL, and the 18-item Hepatobiliary Subscale (HS), which assesses disease-specific issues such as pain, appetite, and cramping. The FACT-G is divided into four HRQL domains: physical well-being (7 items), social/family well-being (7 items), emotional well-being (6 items), and functional well-being (7 items). All items have a 7-day reference period and are scored from 0-4 (“not at all” to “very much”), with higher scores indicating better HRQL. Score ranges are 0-28 for physical well-being, 0-28 for social/family well-being, 0-24 for emotional well-being, 0-28 for functional well-being, and 0-72 for HS. All subscale scores from the FACT-G and HS can be summed together to create a total FACT-Hep score, with a possible range of 0-180. The FACT-Hep takes approximately 10 minutes to complete.

Subjects assigned to the SBRT arm will complete the FACT-Hep at baseline/screening, at the time of the second fraction of the SBRT treatment (post treatment prior to discharge), on the last day of treatment (post treatment prior to discharge), 2 weeks after treatment, and at the time of follow-up scans at 3, 6, 9, 12, 15, 18, 21 and 24 months from randomization or until liver transplantation.

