**Table 4: Study Calendar for FOLLOW-UP (Both Arm A and Arm B)**

Follow-up After Initial Treatment Phase					
		3 months (+/- 4 weeks) post randomization	6 months (+/- 4 weeks) post Randomization	Q 3 months to 24 months post- randomization (+/- 4 weeks)	60 days post- transplantation (+/- 2 weeks)
History and Physical Exam		X	X	X	
Weight		X	X	X	
CBC with differential		X	X	X	
AST, ALT, Alk Phos, Bilirubin		X	X	X	
Na, BUN/Creatinine		X	X	X	
INR		X	X	X	
AFP (for HCC)		X	X	X	
Toxicity Notation		X	X	X	
Survival Status		X	X	X	X
MRI or CT of the abdomen  (mRECIST for HCC)		X	X	X	
Chest CT or X-ray 		X	X	X	
MELD-Na CP ALBI assessment		X	X	X	
Assessment of disease progression, recurrence and transplantation status		X	X	X	
HRQL 		X	X	X	
Mortality and Morbidity					X

 Scans will be obtained in accordance to liver transplantation protocols and timeframes and may not occur within the allotted time frame noted above. This will not be considered a protocol deviation as long as they are performed per United Network for Organ Sharing (UNOS) guidelines.

 HRQL questionnaire: FACT-Hep

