#### 11.1.3.4 Serial imaging

Participants who are listed for liver transplant will undergo serial imaging scheduled in accordance with the 90-day intervals required for cyclical update of the HCC-exception points with UNOS. These images will be used to measure outcomes. For patients not on the transplant list, radiologic imaging will occur

four months ( $\pm$  4 weeks) after randomization and then every three months thereafter until the primary endpoint is met.

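### Patients leave the study at local failure, before the lesion is retreated, so the secondary count of further interventions is cut off by the primary event and compared without time at risk

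*Combined protocol and SAP*

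**What the plan says.** Section 5.6 applies the same rule to both arms: a patient with residual or recurrent disease in a treated lesion "will be considered as having met the primary endpoint of the trial and they are off the study". The sentence that follows allows further local therapy of any kind to that lesion. Section 5.5 says of such treatment: "Any additional ablative treatment, be it to repeat TACE or SBRT or other therapy will be determined at that time". That provides for a decision, not for a record.

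The protocol nevertheless means to count these treatments. Specific Aims 2.0 lists "Number of further interventions". Sections 15.0 and 17.2.3 call the outcome retreatments; 17.2.3 compares the number by t-test and the proportion with any by chi-square. Its closing sentence then sends quantitative outcomes to the HRQL method as well.

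Patients who develop new intrahepatic lesions are handled differently. Under 5.7 they may be treated "per the discretion of the treating providers and will be followed per Table 4 thereafter".

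The nearest row in Table 4 is "Assessment of disease progression, recurrence and transplantation status". There is no row for further interventions.

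**The concern.** The event that ends follow-up is the event that leads to the treatment being counted. Read literally, 5.6 leaves the count made up mainly of new-lesion treatments given before local failure. If sites also record the retreatment that prompts the exit, the count holds at most one such treatment per local failure, and later ones are lost. Which of these happens depends on unwritten site practice.

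Time at risk is unequal by design: the arm with better local control stays on study longer. A t-test on raw counts takes no account of this.

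Other secondary outcomes share the uncertainty. It is unclear whether survival status, explant pathology and 60-day post-transplant outcome are collected for patients who left at local failure and were transplanted or died later.

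**Working it through.** **The passages side by side**

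- Supporting an exit at local failure: 5.6. Section 11.1.3.4 images "every three months thereafter until the primary endpoint is met", but this covers only patients not on the transplant list. Section 17.2.1 names the primary outcome as a source of missing HRQL data.
- Against it: sections 6.0 and 13.2 collect FACT-Hep "at the time of follow-up scans at 3, 6, 9, 12, 15, 18, 21 and 24 months from randomization or until liver transplantation", with no stop at local failure. Table 4 runs survival status to 24 months. Section 11.1.4 images waitlisted patients until transplantation and provides for another ablative round. The off-study list in 12.2 does not include local failure.
- Possible sources for the missing record: 12.2 follows patients given therapy other than TACE or SBRT, but only for progression in the treated lesion. Section 11.1.4 uses the further ablative round only to set imaging times. Neither counts interventions.

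**The plan's own figure**

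The documents give no figure for this endpoint. The event counts in 16.0 do reproduce: 4 × (1.9600 + 0.8416)² / (ln 0.6)² = 120.3 against 120 stated, and 161.1 against 161 for 90% power. The SBRT median is 134 / 0.6 = 223 days. These are therefore sound inputs.

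**Time on study**

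Inputs: medians of 134 and 223 days, 15% yearly dropout and 98 per arm (16.0 and Table 7); a 730-day horizon (17.1). Assumed: constant hazards and 50% transplanted by two years (16.0 says more than 50%, counted from listing).

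Daily hazards:
- local failure: ln 2 / 134 = 0.005173 (TACE) and ln 2 / 223 = 0.003108 (SBRT)
- dropout: −ln(0.85) / 365 = 0.000445
- transplant: ln 2 / 730 = 0.000950

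The totals are k = 0.006568 (TACE) and 0.004503 (SBRT).

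Exit at the event itself:
- mean time on study = (1 − exp(−730k)) / k = 151 days (TACE) and 214 days (SBRT), ratio 1.42
- leaving at local failure = 98 × (failure hazard / k) × (1 − exp(−730k)) = 77 and 65

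Exit at the next three-monthly scan (91.25 days; simulation of 2,000,000 patients per arm) is the main case. Scan-based exit is used because 5.5 says "Progression of disease will be confirmed with imaging done greater than 8 weeks from last treatment date".
- mean time on study: 188 and 245 days, ratio 1.30
- leaving at local failure: 71 and 61 of 98
- transplanted before local failure: about 18 and 23 of 98

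If follow-up continued past local failure, k = 0.000445 + 0.000950 = 0.001395 in both arms. Mean time at risk would be about 458 days in each, with about 43 transplants per arm observed.

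Sensitivity of the 1.30:
- Table 7 accrual (one year, in a two-year study): about 1.25
- half of TACE patients first assessable at six months (assumed): 245 / 203 = 1.21; all of them: 1.13
- 70% transplanted (assumed): 215 / 170 = 1.26, with 62 and 52 leaving at local failure

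**Illustration of the count**

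This assumes equal new-lesion treatment rates in the two arms and one retreatment per local failure. At 0.4 per year in the main case:
- no retreatment recorded: 98 × 188.4/365 × 0.4 = 20.2 (TACE) and 98 × 244.8/365 × 0.4 = 26.3 (SBRT), SBRT/TACE ratio 1.30
- prompting retreatment recorded: 20.2 + 71.4 = 91.6 and 26.3 + 60.9 = 87.2, ratio 0.95
- full count with continued follow-up: 120.5 and 110.1, ratio 0.91

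Over assumed rates of 0.2 to 0.8 per year, the second ratio runs from 0.91 to 1.01 and the third from 0.89 to 0.94.

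**The case against.** A reader might infer that the plan will make SBRT look worse on this endpoint. The documents do not support that. It needs two readings at once: that the retreatment prompting exit goes unrecorded, although the plan evidently means to count retreatment, and that new-lesion therapy counts as retreatment, which 17.2.3 leaves open. If the prompting retreatment is recorded, the distortion is modest, as the ratios above show. With no intervention rates in the documents, any false-positive rate for the t-test would rest on assumed inputs, so none is offered as evidence.

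A reader might also infer that the count is empty or that exit at local failure is settled. Neither holds: treatment of new lesions under 5.7 falls within Table 4 follow-up, and the sections listed above disagree on the exit.

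The time model can be challenged too, and part of this stands:
- TACE may start up to 3 weeks after randomization, sessions are 4 to 6 weeks apart, and confirmation comes more than 8 weeks after the last. Two sessions can thus run to 3 + 6 + 8 = 17 weeks and three to 23, past a 13-week scan. This delays exit in the TACE arm only, hence the 1.13 to 1.21.
- Section 16.0 says its hazard ratio already allows for three-monthly follow-up, so rounding the medians up to the next scan may double-count that delay. The exit-at-event figures avoid this and give a larger ratio.

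Finally, absence from Table 4 is weak evidence by itself. Explant pathology has no row either, and the operations manual, worksheets and data capture system are not available here. They may ask for retreatments. The protocol would still instruct sites that the patient is off study.

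**Conclusion.** The concern stands for secondary endpoints. Following 5.6 as written truncates the count of further interventions at the primary event, and the planned t-test ignores the unequal time at risk that results. About 71 of 98 TACE and 61 of 98 SBRT patients would leave at local failure, with mean time on study of about 188 against 245 days. The ratio of 1.30 ranges from 1.13 to 1.42 with the timing of exit, accrual and TACE sessions. These figures rest on the plan's medians and dropout, constant hazards and an assumed transplant rate; they need no assumed intervention rate. The size and direction of bias in the count itself remain illustrative.

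The primary analysis is not affected, because the exit occurs once its event has been recorded. Nor do the documents show a corresponding defect in the toxicity comparison. This should be fixed, mainly because retreatments not recorded during the trial may be hard to recover later.

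**What to change.** 1. Reconcile 5.6 with 6.0, 11.1.3.4, 11.1.4, 12.2, 13.2, 17.2.1 and Table 4 by separating the end of protocol treatment from the end of data collection. After local failure, keep recording later liver-directed and systemic treatments (a new row in Table 4), survival status, explant pathology and 60-day post-transplant outcome, until 24 months, death or 60 days after transplant. State whether the endpoint counts treatment of treated lesions, of new lesions, or both. No treatment rule needs to change.
2. In 17.2.3, name one method for this count. A rate over follow-up time is preferable: Poisson regression with a log follow-up offset and robust standard errors. This is secondary to step 1, since with continued follow-up mean time at risk is about the same in both arms.

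The cost is a protocol amendment and modest chart-review data entry after local failure. Step 2 alone is a change of wording.
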